Title Page

Study Title: *Accommodative Behaviors in Multifocal Contact Lenses*

NCT Number: 06064617

Date of Document: Approved by IRB on Nov 30, 2023, Uploaded to Clinical Trials.gov on 08/18/2025

Research Protocol

Accommodative Behaviors in Multifocal Contact Lenses

Study Objectives:

The purpose of this study is to determine if accommodation differs with center near and center distance multifocal contact lenses

Background and Rationale:

Soft multifocal contact lenses are used for a variety of reasons in patient care. Multifocal contact lenses are most often used to correct presbyopic vision by providing a range of clear vision at both distance and near (Chu and Huang, 2010). Multifocal contact lenses correct vision at different distances by introducing a power gradient over the eye. They are designed using center near or center distance designs. For center near designs, the near addition is placed in the center of the lens, and the power becomes more negative in the periphery. Conversely, for center distance designs, the distance prescription is placed in the center, and the power of the lens becomes more positive in the periphery in order to provide the near addition. Center near and distance designs have varying advantages and disadvantages for presbyopic vision correction, so a fitter may choose a specific design based on a patient's individual visual needs. Generally, it is thought that center near designs provide the most accommodative relief and superior near vision because the near addition is centered in the pupil and able to allow maximum near correction, even with miotic pupil size changes associated with accommodation.

There is growing use of soft multifocal contact lenses to slow the progression of myopia in juvenile populations (Walline, Walker, Mutti, et al., 2020). When used for myopia management, the power gradient of a soft multifocal contact lens is utilized to, hypothetically, alter how light focuses in the eye and influence eye growth. Specifically for myopia management, center distance multifocal designs are used. A center distance contact lens optically corrects for the distance refraction in the center of the lens (providing a clear distance image to the macula) while the peripheral portion, with its increasing plus power, generates myopic peripheral defocus. This change in peripheral image focus is thought to provide an optical "stop" signal for axial elongation and myopic progression (Berntsen and Kramer, 2013; Ticak and Walline, 2013; Walline et al., 2020). For myopia management, therefore, multifocal contact lenses are not being used to correct vision or influence accommodation. There have been conflicting reports as to how/if children accommodate normally while wearing multifocal contact lenses. (add some citations here, probably similar to below)

Plus lenses, or add powers, in spectacles are often used in the management of accommodative and binocular vision disorders (Scheiman and Wick, 2008). An add power, or plus lens, relieves accommodative demand. There is conflicting evidence on

whether the add power in soft multifocal contact lenses can be used to manage accommodative and binocular vision disorders (Gong, Troilo and Richdale, 2017; Jimenez, Durban and Anera, 2002; Kang, Fan, Oh, et al., 2013; Madrid-Costa, Ruiz-Alcocer, Radhakrishnan, et al., 2011; Tarrant, Severson and Wildsoet, 2008). Some case reports demonstrate benefits of multifocal contact lenses in accommodative insufficiency and convergence excess but the evidence is not clear and many previous studies utilize lenses that are not readily used anymore (Rodgin, 2009; Weissman, Barr, Harris, et al., 2006). Studies show that soft multifocal contact lenses alter accommodation in participants who wear lenses, but most studies use center-distance lens designs, which is the most commonly used lens for myopia management (Gong et al., 2017; Madrid-Costa et al., 2011; Tarrant et al., 2008).

Most studies that have evaluated accommodative ability and function while wearing soft multifocal contact lenses have examined center distance lenses. Because center distance lenses are used for myopia management, the interest has been to determine if children maintain normal accommodative function while wearing the lenses.

Accommodative function while wearing center near lenses has likely not been studied often because these lens designs are used most in presbyopic populations who have no or waning accommodative ability and are using the lenses, specifically, to account for that accommodative inability.-Knowing how spectacle lenses with add powers effectively treat some binocular vision and accommodative disorders and understanding how center near multifocal contact lenses correct presbyopic vision, it is reasonable to hypothesize that center near multifocal contact lenses may provide a greater therapeutic effect for accommodative and binocular vision disorders than center near designs because the central portion of the lens is the addition power, unlike the center-distance lens designs. This study will aim to determine how accommodative function varies with center distance and center near multifocal contact lenses.

Procedures:

Research Design

This study will be an observational single-center investigation using a cross sectional design and each subject will undergo two test sessions.

Sample

The sample size necessary for this study is 20 subjects. The sample size calculation was completed using effect size with standard deviation values from previously published objective accommodative difference between center-distance multifocal contact lenses and single vision contact lenses, which found about $1.0\text{ D} \pm 0.53\text{ D}$ difference (Gong et al., 2017). In order to detect a 0.5 D difference in accommodative amplitude between center-distance and center-near contact lenses with 90% statistical power, a sample of 14 participants is required. Because a study investigating this hypothesis has not been performed in the past, we will enroll an additional 6 patients to account for unknown variability in the data.

Eligibility Criteria are:

- Ages 18 to \leq 30 years old
- Acuity of 20/25 or better in both eyes with habitual contact lens prescription
- No history of ocular disease or active ocular inflammation
- No history of ocular or refractive surgery
- No current history of rigid contact lens wear
- Astigmatism \leq 1.00 D
- Free of binocular vision disorder (strabismus, amblyopia, vergence dysfunction, accommodative dysfunction)
- No prior or concurrent participation in myopia control or use of low dose atropine, multifocal contact lenses
- No use of any medications suspected to affect accommodation

If a subject presents with conditions such as uncorrected refractive error or pathology, an appropriate referral will be made.

Potential participants will be recruited in the following manners:

- Word of mouth by the investigators among employees and visitors to the College of Optometry
- Flyers
- Email announcements distributed to the faculty, staff, and students at OSU
- Electronic advertisement in the OSU Healthbeat
- Phone calls to potentially eligible participants who are identified from a review of clinical records at the College of Optometry to identify those who wear soft contact lenses.

Measurement

The primary measurement of interest is accommodation, which will be quantified using the following techniques:

Objective Accommodative Amplitude: This non-invasive technique quantifies the total focusing ability of the eye using methods that are commonly used clinically. The refractive power of the eye will be measured with the Grand Seiko autorefractor (a commercially available instrument) while study participants view a 20/30 sized letter at multiple stimulus positions (ranging from optical infinity to 20cm). Ten repeated measures will be collected at each stimulus position. For all measurements, participants will wear an eye patch over their left eye and view the letter target with their right eye while keeping their chin in a chinrest and forehead against the forehead rest. The Grand Seiko autorefractor uses infrared light to obtain refractive measures of the eye and the procedure is non-invasive. The following distances are where accommodation will be assessed: 2.5 D (40 cm), and 4 D (25 cm), and 5 D (20 cm). Because multifocal contact lenses can interfere with the optics and readings of an autorefractor, the multifocal will only be worn on the left eye during this testing. The patient's habitual

contact lens with distance only will be on the right eye. An infrared wratten filter will be placed over the right eye, so that the left eye (with the multifocal) will influence accommodation and readings can be obtained from the right eye.

Subjective Accommodative Amplitude: This technique quantifies the nearest position of clear focus using a method that is the standard technique used in a routine eye examination whereby the participant will be asked to view a row of 20/30 letters first held in close proximity to the eye (approximately 2-3 cm) and then pulled away from the eye along a near point rod. The participant will be instructed to report the moment when the letters first become blurred. The measurement will be repeated three times and averaged and the individual findings compared to published age norms for classification of reduced or adequate accommodative amplitude (Hofstetter, 1944).

Accommodative Accuracy: This technique determines the accuracy of the eye to focus at a near viewing distance. A handheld light and loose trial spectacle lenses are used to quantify the focusing position of the eye while the participant views letters printed on a card. The lenses are held in front of the participant's eye and the light shown quickly across the eye from arm's length.

Accommodative Facility: This technique determines the ability of the eye to quickly focus and relax, which is often needed for visual demands in a classroom. Participants will view a 20/30 letter at 40 cm. The examiner will then place ± 2.00 D flipper lenses in front of the patient's eye (plus or minus). Once the participant clears the letters, they will state "clear" and the examiner will flip to the other side. The number of flips per minute will be recorded.

Detailed Study Procedures

The study will enroll 20 participants from 18-30 years old. The study consists of two days of office visits to the OSU College of Optometry (a baseline visit, and then a second visit on another day with center-distance and center-near contact lenses). Participants will complete the study visits in the Fry Hall clinic research Lab.

Baseline Exam:

- Questions regarding participant demographics, medical history, ocular history, medication use, and refractive error (glasses and contacts) if known.
- Visual Acuity – participants identifying letters to assess visual acuity at distance and near.
- Contrast Sensitivity – participants identifying letters to identify contrast sensitivity at 50 cm.
- Pupil Size – determination of pupil size using a ruler to measure diameter in millimeters in light and dark.
- Ocular alignment:
 - Cover Test - participants viewing a letter or picture while an investigator covers the eyes with a cover paddle and assessed eye alignment.

- Modified Thorington - Measured at distance and near.
- Near Point of Convergence – participants viewing letters while they are moved closer to the eyes to assess convergence movements.
- Stereopsis – participants wearing 3D glasses and identifying shapes in a book to assess depth perception.
- Accommodation - Measures of accommodation will be performed in the following order using the protocols described above under “Measurements”:
 - **Push-up method** - Accommodative amplitudes of accommodation will be measured in the right eye only, 3 times.
 - **Monocular estimation method (MEM)** - This will be measured at 40 cm, in the right eye only.
 - **Accommodative Facility** - Accommodative facility (in cycles/minute) will be measured with ± 2.00 D flippers in the right eye only and binocularly.
 - **Grand Seiko WR-5100K** – Refractive Error will be measured at several points:
 - 0 D (distance)
 - 2.5 D (40 cm)
 - 4 D (25 cm)
 - 5 D (20 cm)
- Refractive Error Assessment – Non-cycloplegic central refractive error (with and without contact lenses). Non-cycloplegic refractive error will be assessed with the Grand Seiko WR-5100K. This will be done with and without Biofinity sphere contact lenses (that is the same prescription as the participant’s habitual contact lens prescription). An average of 10 readings will be calculated (both with and without habitual correction).
- Dilation – participants will be dilated with 1% tropicamide. They will receive 2 drops, 5 minutes apart.
- Cycloplegic Central Refractive Error (without contact lenses). Cycloplegic refractive error will be assessed with the Grand Seiko WR-5100K. This will be done without contact lenses on. An average of 10 readings will be calculated.

Second Visit

- At the second visit, participants will repeat measurements completed at the first examination (except for dilation/cycloplegia) with a center-distance and center-near Biofinity multifocal contact lens (both with +2.50 D add). The order will be randomized for each participant. The multifocals will be worn binocularly for all testing except for autorefraction, so that the optics of the contact lenses will not interfere with measurements.

The total time for each study visit will be no more than 90 minutes.

Study Risks

The risks involved with the participation of this study are no greater than that incurred in a routine eye exam with dilation. The side effects that participants might experience are blurred vision (that generally affects near viewing more than distance), and light sensitivity. Previous studies suggest that the side effects of both concentrations are minimal and do not impede activities of daily living. These drops will only be instilled one time at one visit and side effects should wear off within 4-6 hours. All other study procedures are non-invasive and only involve lights as the participant places his/her chin on a chinrest and looks straight ahead.

Data Collection and Participant Confidentiality

Data will be collected on a paper study form that includes only the participant's study ID. Study measures obtained with the autorefractor will be printed from the instrument and the participant's study ID written on the print-out. The print-outs will then be taped to the paper study form and later scanned into pdf format for storage on the Investigator's computer. No personally identifying information will be stored on the paper datasheet, or in the generation of the scanned pdf. Signed consent/assent/parental permission documents will be kept separate from the study data sheet in a binder in the Investigator's locked laboratory, accessible only to the study team. The link between the study ID and the participant's personal information will be maintained on the signed consent documents.

Internal Validity

There are no threats to internal validity. All procedures performed in the examination are standard procedures that have been performed frequently in other studies. While this project is assessing measurements in one population, there is limited threat to external validity because this is a project of instrument comparability and repeatability and is not intended to make generalizations about the population as a whole.

Data Analysis

Repeated measures analysis of variance (Repeated measures ANOVA) will be completed with measurement environment (single vision CL, center-distance CL, center-near CL). If differences are detected in lens type (center-distance, o center-near), a post-hoc analysis will take place.

Bibliography:

Berntsen, D.A. & Kramer, C.E. (2013). Peripheral defocus with spherical and multifocal soft contact lenses. *Optom Vis Sci*, 90, 1215-24.

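### Autorefraction is given two incompatible set-ups (left eye patched, or left eye viewing through the multifocal); splitting them by visit confounds single vision versus multifocal with set-up

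*Combined protocol and SAP*

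**What the plan says.** The Measurement section makes accommodation the primary measurement of interest and lists four techniques. The first, Objective Accommodative Amplitude, is autorefraction. Its paragraph opens with one arrangement: "For all measurements, participants will wear an eye patch over their left eye and view the letter target with their right eye". It closes with another. Because a multifocal disturbs the autorefractor, "the multifocal will only be worn on the left eye during this testing"; the right eye keeps its habitual distance lens behind an infrared filter, "so that the left eye (with the multifocal) will influence accommodation and readings can be obtained from the right eye".

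The Baseline Exam section refers staff back to these procedures and lists readings at 0, 2.5, 4 and 5 D. The Second Visit section has the baseline measurements, apart from dilation, repeated with each multifocal, and adds: "The multifocals will be worn binocularly for all testing except for autorefraction". On the sequence of the two multifocals it says: "The order will be randomized for each participant". Detailed Study Procedures describes the visits as "a baseline visit, and then a second visit on another day with center-distance and center-near contact lenses", so single vision is always measured first, on a different day.

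Data Analysis enters single vision, center-distance and center-near as three levels of one repeated measures ANOVA factor. It does not say whether the response is the raw reading or the change from 0 D. The Sample section powers center-distance versus center-near for 0.5 D at 90%, giving 14 participants (20 enrolled), with 0.53 D as the standard deviation.

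**The concern.** There are two layers.

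First, the instructions conflict. If the left eye is patched, the left-eye multifocal cannot influence accommodation. The Second Visit section exempts autorefraction from binocular lens wear, but it neither withdraws the patch nor assigns a set-up to a visit.

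Second, the natural way to reconcile them has a cost. With the patch at baseline and the filter at the second visit, single vision is a direct reading with the right eye viewing. Both multifocals are consensual readings, taken through a filter with the left eye viewing. Set-up then changes exactly where the lens changes from single vision to multifocal, and no analysis of these data can separate the two. An overall ANOVA result, or a single-vision contrast, could reflect viewing eye, filter or type of reading instead of the lens. The Internal Validity section recognises no such threat.

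Only autorefraction is affected. The other three techniques use multifocals worn binocularly.

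**Working it through.** **1. The two instructions side by side**

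| | Patch instruction | Filter instruction |
|---|---|---|
| Left eye | covered | views through the multifocal |
| Right eye | views the target | behind the filter, measured |
| Stated scope | all measurements | this same test |

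**2. What each reading implies**

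- *Both followed literally.* The left eye is covered and the right eye wears the habitual distance lens behind a filter meant to hand viewing to the left. Neither multifocal is in the viewing path, so the expected center-distance versus center-near difference is 0 D.
- *Patch at baseline, filter at the second visit.* The two multifocals share visit, set-up and randomized order, so their comparison is sound. Single vision differs from both in set-up as well as lens.
- *Filter at both visits.* There is no set-up confounding, but the patch sentence then has no effect anywhere.

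**3. The plan's own figure**

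Inputs: difference 0.5 D and SD 0.53 D (Sample section), taking 0.53 D as the SD of the paired difference. Alpha is not stated; 0.05 two-sided is assumed. Paired t-test, noncentrality = (0.5/0.53)·√n:

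- n = 13: power 87.7%
- n = 14: (0.5/0.53)·√14 = 3.53, power 90.3%
- n = 20: (0.5/0.53)·√20 = 4.22, power 97.9%

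The stated 14 reproduces.

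**4. Size of the confounding under the split-by-visit reading**

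Further assumptions: SD 0.53 D for every pairwise difference, sphericity, n = 20, no lens effect, raw readings analysed, and a constant set-up offset b on one of the three levels. The documents give no value for b, so a range is shown.

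- Residual variance: 0.53²/2 = 0.14045.
- Sum of squared deviations of the three means: (2/3)b².
- ANOVA noncentrality: λ = 20·(2/3)b²/0.14045 = 94.93·b², referred to F(2, 38).
- Paired test of single vision versus one multifocal, unadjusted: noncentrality (b/0.53)·√20.

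| Offset b (D) | λ | ANOVA rejects | Paired test rejects |
|---|---|---|---|
| 0.1 | 0.95 | 12.2% | 12.6% |
| 0.2 | 3.80 | 37.0% | 36.1% |
| 0.3 | 8.54 | 71.1% | 67.1% |
| 0.4 | 15.19 | 92.8% | 89.3% |
| 0.5 | 23.73 | 99.1% | 97.9% |

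A separate simulation (20,000 runs per setting) gave ANOVA rejection of 5.2%, 12.4%, 54.3% and 99.0% at offsets of 0, 0.1, 0.25 and 0.5 D.

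**5. Center-distance versus center-near under the same reading**

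With offsets from 0 to 0.5 D (40,000 simulated trials per setting), type I error was 4.9% to 5.3% and power for 0.5 D was 97.8% to 98.0%. The offset is common to both lenses and drops out.

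**6. If change from 0 D is analysed**

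A constant offset is present in both the near reading and the 0 D reading, so it cancels; simulated ANOVA rejection was 4.8% to 5.0%. An offset that varies with stimulus distance would not cancel.

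**The case against.** The strongest reply is that a sensible examiner would not patch the eye wearing the multifocal. The filter arrangement is described in detail with its purpose, and a specific instruction normally overrides a general one. On that view the second-visit procedure is clear and needs only a wording correction. This stands as far as it goes: the 0 D outcome is a worst case that contradicts the evident intent. It does not settle which set-up applies at baseline.

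The study's objective and its power calculation also concern center-distance versus center-near, which survives the split reading intact. No section states a single-vision hypothesis. That is correct and limits the weight of the point. Single vision is nevertheless a level of the only planned ANOVA, so a set-up effect enters the overall test.

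The rejection rates are open to challenge too. The offsets have no source in the documents, and the largest equals the whole target difference. The Sample section cites about 1.0 D between center-distance and single vision; at that size λ is about 94.9 and the ANOVA rejects more than 99.9% of the time with no offset. This objection stands in part: if a real effect that large exists, the practical harm is a biased single-vision estimate, not a false rejection. The confounding remains.

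Change from 0 D is arguably the natural response for an amplitude, and it would remove a constant offset. The plan does not specify it.

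Finally, the filter could be intended at both visits. That would avoid the problem, but the text does not say so, and the patch sentence would have to go.

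**Conclusion.** The concern holds and should be fixed. The paragraph is wrong as written: its two arrangements cannot both be followed, and no other section reconciles them. That conclusion rests on the text alone.

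The confounding is conditional on the patch being used at baseline and the filter at the second visit, the most plausible reading but not a stated one. Under it, center-distance versus center-near is unaffected, while the single-vision contrasts and the overall ANOVA cannot be attributed to the lens. How much this matters depends on an unknown offset and an unspecified response. The 12% to 99% range illustrates sensitivity under the stated assumptions; it does not predict this study's error rate.

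**What to change.** - State, for each visit and lens, which eye is covered, which views the target, which is filtered and which is measured.
- Remove the left-eye patch from the lens-comparison readings and use one set-up for all three lenses: left eye uncovered and viewing through the test lens (single vision, center-distance or center-near), right eye in the same distance lens behind the filter and measured.
- Define the analysed response as the change from the 0 D reading already listed in the Baseline Exam section. The common set-up is still needed, because an offset that varies with distance would not cancel.
- If data have been collected, document the set-up used at each visit. If the set-ups differed, base the conclusion on center-distance versus center-near and label the single-vision contrast as confounded with set-up.

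The cost is rewording plus one procedural change, moving the baseline single-vision readings to the filter set-up. The equipment and lenses are already in the study and no participants are added. Two drawbacks remain. Single vision is still measured on a separate day outside the randomized order, so that contrast is improved but not fully clean. Change from 0 D also brings in the measurement error of the 0 D reading.

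### The study is sized on accommodative amplitude, but two techniques bear that name, none is named primary, and the likelier one stops at a 5 D stimulus with no rule for deriving an amplitude

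*Combined protocol and SAP*

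**What the plan says.** **Sizing (Sample).** The target reads "In order to detect a 0.5 D difference in accommodative amplitude between center-distance and center-near contact lenses with 90% statistical power", and 14 participants are said to suffice; 20 are to be enrolled. The variability is taken from "standard deviation values from previously published objective accommodative difference between center-distance multifocal contact lenses and single vision contact lenses", given as about 1.0 D ± 0.53 D. The sizing sentence does not say whether the amplitude is the objective or the subjective one.

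**Primary measurement (Measurement).** "The primary measurement of interest is accommodation, which will be quantified using the following techniques". Four techniques follow with equal standing: objective amplitude, subjective amplitude, accuracy and facility.

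**Objective test (Objective Accommodative Amplitude).** Its purpose is described thus: "This non-invasive technique quantifies the total focusing ability of the eye using methods that are commonly used clinically". On the stimuli: "The following distances are where accommodation will be assessed: 2.5 D (40 cm), and 4 D (25 cm), and 5 D (20 cm"). The same paragraph gives the range as optical infinity to 20 cm, with ten readings per position. The Baseline Exam list says "Refractive Error will be measured at several points" and includes 0 D. The Second Visit repeats the baseline measurements, apart from dilation and cycloplegia, with each multifocal.

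**Which eye (same paragraph).** Participants patch the left eye for all measurements and view with the right. Later, the multifocal is on the left eye, an infrared filter covers the right, and the left eye is said to influence accommodation while the right is read.

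**Subjective test and facility.** The subjective amplitude is the average of three readings, with no 5 D limit. Facility is taken with "flippers in the right eye only and binocularly".

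**Analysis (Data Analysis).** "Repeated measures analysis of variance (Repeated measures ANOVA) will be completed with measurement environment (single vision CL, center-distance CL, center-near CL"), followed by a post-hoc analysis if lens types differ. No dependent variable, stimulus level, significance level or multiplicity rule is given.

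**The concern.** A power statement is a property of one defined outcome and one test. Here the outcome is a label shared by two techniques. The one that the SD source favours is described as measuring something its stimulus range does not reach in everyone. Three things are at stake.

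- **Choice of main result.** With no outcome fixed, whichever amplitude shows a lens difference could be presented as the main finding after the data are seen.
- **Meaning of the objective result.** Someone whose response is still rising at 5 D has no observed maximum. A lens difference at 5 D is then a difference in response to that demand, and reporting it as a difference in amplitude would overstate it.
- **Whether the objective comparison works at all.** If the left eye is patched, the multifocal on it cannot drive accommodation. The readings would then come from a right eye wearing its habitual single-vision lens, and would carry no information on lens design.

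**Working it through.** **1. Reproduce the stated sample size.** Inputs from Sample: difference 0.5 D, SD 0.53 D, power 90%. Assumed, because not stated: paired t-test, two-sided 5%. The noncentrality is (0.5/0.53)·√n, and power comes from the noncentral t with n − 1 degrees of freedom.

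| n | Noncentrality | Power |
|---|---|---|
| 13 | 3.40 | 87.7% |
| 14 | 3.53 | 90.3% |
| 20 | 4.22 | 97.9% |

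The stated 14 reproduces. The fault is in the outcome, not the arithmetic.

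**2. Count the candidates for the sized outcome.** The sizing is in dioptres and uses the word amplitude. Facility is recorded in flips or cycles per minute, so a 0.5 D target cannot apply to it. MEM is labelled accuracy. Two candidates remain: objective and subjective amplitude. The SD source favours the objective one but does not name it as the outcome.

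**3. Size of the open choice.** Assume 5% per test and that either candidate could be declared the main result. For k independent tests the chance of at least one false positive is 1 − 0.95^k. For correlated tests I used equicorrelated normal statistics, with assumed correlations.

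| Outcomes that count | Independent | Correlation 0.5 | Correlation 0.9 |
|---|---|---|---|
| 2 amplitudes | 1 − 0.95² = 9.75%, about 9.8% | 9.1% | 7.0% |
| All 4 techniques | 1 − 0.95⁴ = 18.5% | 15.6% | 9.4% |

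**4. What the objective test delivers.** Readings exist at 0, 2.5, 4 and 5 D. A maximum response, the response at 5 D, the change from 0 D and a slope are all possible summaries, and none is chosen. Averaging of ten readings is stated for the refractive error assessment but not for the readings at each demand. The documents give no expected amplitudes for ages 18 to 30, so the number still rising at 5 D cannot be computed.

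**5. Eye statements side by side.** Left eye patched for all measurements, right eye viewing; against left eye wearing the multifocal and influencing accommodation, right eye behind an infrared filter. Both cannot hold for the multifocal readings.

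**6. How far the SD carries over.** The 0.53 D comes from center-distance versus single vision; the sized contrast is center-near versus center-distance. Solving the step 1 power formula for SD at n = 20 gives 0.654 D for 90% power and 0.757 D for 80%. For illustration, assume each multifocal-minus-single-vision difference has SD 0.53 D and the two differences correlate at r. The SD of the sized contrast is then 0.53·√(2(1 − r)).

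| r | SD | Power at n = 20 |
|---|---|---|
| 0 | 0.75 D | 80.8% |
| 0.25 | 0.65 D | 90.4% |
| 0.5 | 0.53 D | 97.9% |

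**The case against.** The best defence is that the sizing sentence already narrows the outcome. It speaks of amplitude in dioptres for one lens contrast, with an SD from an objective measure, so a fair reader would take the objective test as primary. That stands as far as it goes, and it rules out a stronger reading that a reader might infer: that any of four techniques, or seven measures once stimulus levels and the two facility results are counted separately, could equally become the sized result. The 18.5% figure applies only if all four count and are independent. Counting the 2.5, 4 and 5 D readings as separate chances of success would also treat one test as three. But an implied test still lacks a stimulus level and a derivation rule, and its description does not match its range.

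The 0 D reading is not missing either. The paragraph listing assessed distances omits it, but Baseline Exam includes it and Second Visit repeats those measurements. A change from 0 D can be computed; the plan just does not say that it will be.

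The subjective test has a scoring rule and no 5 D limit, so the study does measure an amplitude. That is true, but the plan does not make it primary and the SD does not come from it.

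Finally, the study is small, calls itself observational, and addresses a question it says is new. That argues against demanding formal multiplicity adjustment across supporting measures. It does not excuse a 90% power claim with no defined outcome.

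**Conclusion.** The concern holds in this form: the sized outcome is ambiguous between two amplitudes. The favoured one measures response at fixed demands up to 5 D rather than total focusing ability in anyone still rising there. The analysis section does not settle the matter. The patch and left-eye statements conflict, and until they agree the objective lens comparison cannot be interpreted.

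The size of the open choice is modest: 9.8% if independent, falling to 7.0% at correlation 0.9, against a nominal 5%. This assumes 5% per test and that either amplitude could be declared the main result.

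The documents do not support a claim that the sample size is wrong, nor that the 5 D limit spoils the study. The stated 14 reproduces under a two-sided 5% paired t-test, and a lens difference at a fixed demand remains measurable once the eye statements are reconciled. The change should be made, because without it the power statement belongs to no defined result.

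**What to change.** 1. Reconcile the statements in Objective Accommodative Amplitude on which eye is patched and which eye drives accommodation.
2. Name one primary outcome and one deciding test. One example is the objective response at the 5 D stimulus, taken as the mean of the ten readings minus the mean at 0 D, compared between center-near and center-distance by a single paired contrast at two-sided 5%. A lens-by-demand model over 2.5, 4 and 5 D, and the comparisons with single vision, would then be supporting analyses.
3. Restate the sizing sentence for that outcome and drop the amplitude and total-focusing wording for this test. State that the 0.53 D SD comes from a center-distance versus single-vision comparison, and that 20 participants keep 90% power up to an SD of about 0.65 D and 80% up to about 0.76 D.
4. Label the push-up, MEM and facility measures secondary or exploratory.

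The cost is wording and analysis plan only, and N stays 20. The downside is that the other techniques lose primary status. If the sponsor prefers the subjective amplitude as primary, it needs its own SD, which the documents do not give.
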